In summary, 9 patients (37.5%) treated with external fixation required re-operation (2 for deep infection, 3 for malalignment, 4 for delayed union) versus one re-operation (3.8%) for patients treated with intramedullary nailing. While early results from this pilot study predict a clinical advantage for intramedullary nailing over definitive external fixation, we feel the small sample size, limited follow-up, and lack of functional outcomes data warrant further empirical investigation. Most importantly, this pilot study, conducted by a Tanzanian primary investigator, demonstrates the viability of success for completing a larger randomized, prospective clinical trial in Dar es Salaam, Tanzania.

3. Specific Aims

Study Objective: To determine the optimal management of severe open tibial fractures in Sub-Saharan Africa in order to reduce long-term disability, limit the economic impact of injury, and avoid resource costs of reoperation.

Specific Aims

1) Compare the all-cause reoperation rate for AO/OTA Type 42 open tibial shaft fractures treated with initial intramedullary nailing versus external fixation at Muhimbili Orthopaedic Institute in Dar es Salaam, Tanzania.

- 2) Compare rates of secondary clinical endpoints including postoperative superficial and deep infection, clinical union, radiographic union, malunion, and health-related quality of life with minimum one year follow-up.
- 3) Identify prognostic factors related to the patient, injury, or management protocol that impact the reoperation rate, return to work, and health-related quality of life.

Study Null Hypothesis: There is no difference in the all-cause re-operation rate comparing reamed intramedullary nailing and external fixation for the initial treatment of OTA 42 Type 42 open tibia fractures

4. Methods

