- b. "Describe where you live" is a free text box. Provide as much detail as possible so that it may be possible to find the patient later on if the phone numbers no longer work and they are lost to follow-up.

Additional Numbers	
Ward leader phone number (if available)	
Ward leader name	
Record additional phone numbers here. For each number, include the following:	

 - Number - Name - Relationship (Self, Family, Friend, or Other) 	Expand

Address

Describe where you live:

Expand

Describe where you plan to spend most of your time during recovery

Expand

Email

E-mail

If available

9. Antibiotics

- a. Once the patient has provided consent to participate in the study, they should receive antibiotics as quickly as possible if they have not yet.
- b. If the patient received antibiotics at another hospital but then came to MOI and was changed onto a study antibiotic regimen, choose "other" and record the details of all antibiotics given since the time of injury

Antibiotics

Date and time of first dose of antibiotics administered after the injury

* must provide value

Now D-M-Y H:M

Insert date and time by clicking on the calendar image above

Was the first dose of antibiotics administered at MOI?

* must provide value

Yes

No

reset

What antibiotic regimen is the patient starting on at MOI?

* must provide value

Ceftriaxone only

Ceftriaxone + gentamycin

Ceftriaxone + gentamycin + metronidazole

Other

reset

If "Other", describe the following:

- Type of antibiotic
- Dosage
- Length of administration
- Reason of using a non-standard antibiotic

Expand

Standard Study Antibiotics Regimen

- None or Mild Contamination: Ceftriaxone (1g every 24hr for 2 days)
- Surface Contamination (not ground in): Ceftriaxone (as above) + Gentamycin (80mg every 12hr for 2 days)
- Severe or High-Risk: Ceftriaxone + Gentamycin (as above) + Metronidazole (500mg every 8hr for 2 days)

10. Tetanus prophylaxis

- a. All patients should have tetanus prophylaxis. This is usually in the form of a shot given in childhood with repeated shots every few years. If the patient does not remember or knows they have never received a tetanus shot, work with the National Hospital Emergency physicians to ensure the patients get the shot as soon as possible. This is most important for the patient's health, but also important for the study.

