6.4 Post-Op Discharge

This form is to be filled out the morning after the patient's operation. This information is to be found in the patient's record which will be with the nurses in the ward.

1. Temporary Fixation using Damage Control

- a. Report whether or not temporary fixation was performed. If there is a mismatch between what was said about temporary fixation in the Intra-op/Randomize Form, warning messages will occur asking you to double check your answer.
- b. Note that if temporary fixation was not performed, the option to record the date of temporary fixation will not appear.

Temporary Fixation

Was damage control using a temporary external fixator performed? Yes No

* must provide value reset

The intra-operative form indicates that the patient **DID** require temporary fixation. Please review the patient's chart. Contact [name] if there is any confusion.

The intra-operative form indicates that the patient **DID NOT** require temporary fixation. Please review the patient's chart and contact [name] if there is any confusion.

What date was temporary fixation performed? Today D-M-Y

* must provide value

Format is DD-MM-YYYY. Insert date manually, by clicking on the calendar image above, or press "Today" if applicable

2. Date of definitive treatment

- a. This is a critical study question because the reports for follow-up visits is based on this question
- b. If there is a mismatch between the type of definitive option stated in this form and what the patient was randomized to, a warning message will appear
- c. The size of the interlocking screws does not have to be recorded.

Definitive Treatment	
Date of Definitive Operation	   <small>Format is DD-MM-YYYY. Insert date manually, by clicking on the calendar image above, or press "Today" if applicable</small>
This is a key study question <small>* must provide value</small>	
What type of definitive operation was performed?	
This is a key study question <small>* must provide value</small>	
The incorrect operation was performed. Please notify the review committee immediately.	
The incorrect operation was performed. Please notify the review committee immediately.	
What is the size of the SIGN nail used?	
Number of proximal interlocking screws	 1  2 

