Any IPSILATERAL UPPER extremity injuries?			reset
Any CONTRALATERAL UPPER extremity injuries?			reset
Describe other ipsilateral lower extremity injuries			Expand

Injury Severity Score			
	Yes	No	
Head/Neck (+ Cervical Spine)			reset
Face (+ Facial Skeleton, Nose, Mouth, Eyes, Ears)			reset
Chest			reset
Abdomen (+ Lumbar Spine)			reset
External			reset
Describe head/neck injuries			Expand

5. Antibiotics Check

a. Record any additional antibiotics that were given in the ward and whether or not all the courses of antibiotics the patient was started on were properly completed (all doses were given on time)

Antibiotics Check

Did the patient get started on any other antibiotics while in the ward besides the ones that have already been recorded?

Yes
 No

* must provide value reset

What other antibiotics did the patient receive?

- Type of antibiotic
- Dose
- Timing

Expand

Were all antibiotic courses administered on time and completed?

Yes
 No

This is a key study question

* must provide value reset

Describe which antibiotics were not administered on time or completed.

Expand

Standard Study Antibiotics Regiment

- None or Mild Wound Contamination: Ceftriaxone (1g every 24hr for 2 days)
- Moderate: Ceftriaxone (as above) + Gentamycin (80mg every 12hr for 2 days)
- Severe or High-Risk: Ceftriaxone + Gentamycin (as above) + Metronidazole (500mg every 8hr for 2 days)

b. Pin care information should be given to patients who have an exfix. The protocol is to pour methylated spirited onto the pin 2x a day

Discharge

Has the patient received proper exfix pin care information?

Yes
 No

reset

Please instruct the patient on proper pin-care (pour methylated spirit onto the pin 2x a day)

Afterwards, change the answer to the above question to "Yes".

Has a follow-up schedule been generated for the patient?

* must provide value Yes
 No

reset

Please save this form as "Incomplete" and generate a follow-up schedule for the patient. Afterwards, change the answer to the above question to "Yes".

Time and Date of Discharge

* must provide value Insert date and time by clicking on the calendar image above

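### Two antibiotic data-capture rules conflict with their own fields: prior outside antibiotics force the code *Other* for a study regimen, and course completion is asked on a form timed for the morning after surgery (minor)

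*Protocol*

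**What the plan says.** **Regimen code.** In section 6.1, item 9 (Antibiotics), a mandatory field asks "What antibiotic regimen is the patient starting on at MOI". The choices are ceftriaxone alone, ceftriaxone plus gentamycin, all three drugs, or *Other*. The text box opened by *Other* asks for drug, dosage, length and "Reason of using a non-standard antibiotic". Item 9b covers patients treated elsewhere first: "If the patient received antibiotics at another hospital but then came to MOI and was changed onto a study antibiotic regimen", staff are to pick *Other* "and record the details of all antibiotics given since the time of injury". A separate mandatory yes/no item already records whether the first dose was given at MOI.

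**Theatre additions.** Section 6.2, item 5, codes antibiotics added after debridement as increments: plus gentamycin, plus gentamycin and metronidazole, other, or none.

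**Completion.** Section 6.4 opens with "This form is to be filled out the morning after" the operation. Its Antibiotics Check has a mandatory yes/no item, flagged as key to the study: "Were all antibiotic courses administered on time and completed". The same form asks about antibiotics started in the ward and requires the date and time of discharge.

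**Use.** Aim 3 in section 3 is to "Identify prognostic factors related to the patient, injury, or management protocol that impact the reoperation rate", among other outcomes.

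**The concern.** Item 9b contradicts the field it governs. A patient who had one dose at a district hospital and then starts ceftriaxone alone at MOI is on a study regimen, but is coded as though on a non-standard one. *Other* then mixes truly non-standard regimens with study regimens preceded by outside treatment, and becomes partly a marker of prior care. The increments coded in section 6.2 also lose their coded baseline: plus gentamycin, added to *Other*, says nothing about the total regimen unless the free text is read.

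The second conflict is one of timing. A yes/no item with no option for a course still running sits on a form scheduled for a time when a 2-day course may not have ended.

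Antibiotic regimen is an obvious candidate among the management factors in Aim 3, and completion is the natural measure of adherence. Both would be analysed from values that the manual's own rules make wrong in one case and often premature in the other.

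**Working it through.** The protocol gives no figure to reproduce on this point. The coding half is a comparison of texts; the timing half is dose arithmetic.

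**1. Coding, side by side**

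| Item in section 6.1 | What it captures |
|---|---|
| Regimen field | Regimen started at MOI |
| *Other* text box | Non-standard antibiotic, with a reason |
| Item 9b | *Other* for a patient put on a study regimen after outside antibiotics |
| First-dose item | Whether the first dose was given at MOI |

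The third row cannot be squared with the first two. The fourth already holds the fact that 9b seems meant to preserve.

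**2. Dose times.** Inputs are the regimens in section 5.1 (Antibiotics Administration), each for 2 days. Number of doses = 48 h / interval; last dose = 48 h − interval.

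- Ceftriaxone every 24 h: 2 doses, last at 24 h
- Gentamycin every 12 h: 4 doses, last at 36 h
- Metronidazole every 8 h: 6 doses, last at 40 h

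**3. Course started at admission.** Assumptions: the form is filled at 08:00; the clock time *a* of the first dose is spread evenly over 24 h in half-hour steps; surgery follows *d* hours after the first dose. Then

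hours from first dose to form = 24 × (floor((*a* + *d*)/24) + 1) + 8 − *a*.

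| Delay *d* | Hours from first dose to form | Last dose already due: ceftriaxone / gentamycin / metronidazole |
|---|---|---|
| 0 h | 8.5–32 | 35% / 0% / 0% |
| 12 h | 20.5–44 | 85% / 35% / 19% |
| 24 h | 32.5–56 | 100% / 85% / 69% |
| 36 h | 44.5–68 | 100% / 100% / 100% |

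The trial's own delay from admission to surgery is not given. The nearest figure is from the pilot (section 2.3), where 98% were treated within 24 h of injury. If that refers to surgery and carries over, the first three rows are the relevant ones.

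**4. Course added in theatre.** Here *d* = 0 and the clock starts at surgery, so 8.5–32 h have passed by 08:00. Both 36 h and 40 h exceed 32 h, so the last gentamycin or metronidazole dose is never due. This does not hinge on 08:00: surgery at the earliest on the previous day (00:00) and a form at any time before noon gives less than 24 + 12 = 36 h.

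**The case against.** The strongest reply is that these are two slips of manual wording with little consequence. Much of it stands.

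- A reader might infer that the regimen is lost. It is not: item 9b itself requires every antibiotic since injury to be written down. What is lost is the code. Recovery does depend on staff having noted which drugs were started at MOI, because the box prompts for drug, dosage, length and reason, not place.
- A reader might apply the rule to all referred patients and convert that into a share of patients or reoperations. Item 9b covers only those given antibiotics elsewhere and then moved to a study regimen. Referral is a different field, and the protocol gives the size of neither group.
- A reader might call the completion answer false by instruction. Nothing tells staff to enter an answer they do not have. Courses begin at admission, so some are finished by that morning. The mandatory discharge time means the form must stay open or be reopened. For another item, the form itself tells staff to save it as incomplete and change the answer later.
- Contamination, which guides the choice of regimen, is coded separately in the OTA wound classification. The appendix on antibiotic supply also remarks that little gentamicin was used, so the theatre-added case may be uncommon.

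What does not fall away is that item 9b contradicts its field, and that no sentence tells staff to revisit the antibiotic answers when the discharge time is entered.

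**Conclusion.** The concern holds as a minor data-capture point. The regimen code is misclassified by rule for patients treated with antibiotics elsewhere and then put on a study regimen; the number is unknown. The completion item, if answered when scheduled, is premature for many patients but not all, depending on the delay to surgery. It is always premature for a 2-day gentamycin or metronidazole course added in theatre. The percentages rest on the assumed 08:00 form and an even spread of first-dose times; the theatre result needs only a form filled before noon.

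A reader might fear for the trial's main result. The protocol gives no ground for that: both fields are recorded the same way in both arms, the admission regimen is chosen before randomization, and neither field enters the reoperation outcome or a listed secondary outcome. The effect is confined to Aim 3, where regimen would in any case be confounded with contamination, and to the description of adherence.

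**What to change.** These changes concern recording only and leave treatment untouched.

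1. Reword item 9b so that the coded regimen is the one actually started at MOI, with *Other* kept for non-standard regimens.
2. Record outside antibiotics in a text field that opens when the first-dose-at-MOI item is answered no.
3. Recode existing *Other* records from their free text, preferably by someone who does not see the outcomes. Where the text does not separate outside from MOI drugs, consult the patient file.
4. Reconcile the timing sentence in section 6.4 with the items on its form: the ward-antibiotic and completion items should be answered or confirmed at discharge, when the discharge time is entered.

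The cost is two manual sentences, one branching rule and a one-time recode.

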6.2 Intra-operative/Discharge Form

This form applies to both RCT and cohort patients. But for cohort patients, the randomization module will not appear.

1. Wound measurement

- a. A measurement of the wound should be performed after the patient receives pain medication and after all bandages and dressings have been removed. Take the maximum dimension of the portion that is open, ignoring superficial abrasions
- b. The measurement should be done in centimeters using a ruler rather than visually approximated. Be as precise with the measurement as possible

2. Surgical Debridement and Primary Closure status

- a. Whether or not the surgeon believes the wound can be primarily closed is done after surgical debridement. They will clean up the wound, manipulate the fracture, and see if there is enough skin to close the wound.
- b. If the surgeon believes the patient can be primarily closed, the patient passes the last exclusion criteria check and should remain in the study. If it is a cohort patient, it is up to the surgeon which operation the patient receives. If it is an RCT patient, proceed to the randomization module

Has the wound been surgically debrided?		
<small>* must provide value</small>		
 Yes  No		
reset		
Does the surgeon believe this patient is primarily closeable?		
 Yes  No		
This is a key study question		
<small>* must provide value</small>		

- c. If the surgeon believes the wound is not primarily closeable, the patient needs to be excluded from the study. This is considered an "intra-operative exclusion". This is what the warning message looks like:

Subject is **NOT** eligible for the RCT study anymore.

This patient is considered an "intraoperative exclusion". Save the form as "Complete". Do not change any information that has already been collected.

Subject is **NOT** eligible for the cohort study anymore.

This patient is considered an "intraoperative exclusion". Save the form as "Complete". Do not change any information that has already been collected.

3. Randomization (RCT ONLY)

- a. If the patient is a cohort patient, the following reminder message will appear indicating the randomization module is hidden for these patient

Subject is a **PROSPECTIVE COHORT** patient. The randomization module will not appear. Please complete the remaining questions.

The patient has been enrolled in the wrong study.

The patient **IS** eligible for the RCT but has been enrolled in the COHORT study. Because of this, the randomization window module will not appear.

Please double check the inclusion/exclusion criteria. Do not proceed until this error has been resolved.

- b. For RCT patients, this is what the randomization module appears like. Click on randomize, confirm the warning message, and randomize the patient. The randomization module results are final. Once randomization has been performed, the patient must remain in the study and must receive that operation

THIS IS THE RANDOMIZATION MODULE. ONCE YOU RANDOMIZE, THE RESULTS ARE FINAL

This patient has been randomized to receive:

* must provide value

Date and Time of Randomization

* must provide value

Insert date and time by clicking on the calendar image above

4. Damage Control

- a. If the patient believes that damage control using a temporary external fixator should be performed before the definitive operation that the patient has been randomized to (in the case of RCT patients) or that the surgeon has decided (in the case of cohort patients), then record "Yes". Damage control is usually done in situations where the patient is not hemodynamically stable enough for a full surgery, but it is still better to temporarily fixate the fracture using an exfix.

Variable: random [Branching logic exists]

THIS IS THE RANDOMIZATION MODULE. ONCE YOU RANDOMIZE, THE RESULTS ARE FINAL

This patient has been randomized to receive:

* must provide value

Date and Time of Randomization

* must provide value

Will the surgeon perform "damage control" using an external fixator because the patient is currently too unstable?

* must provide value

The patient will now receive a temporary external fixator and receive the definitive operation at a later date. This is allowed under our study protocol.

Please remember to record the dates of both operations in the post-op/discharge form.

reset

5. At this time, additional antibiotics can be added or removed depending on how much contamination the surgeon believes there to be inside the wound

Does the surgeon believe additional antibiotics are required?

+ Gentamycin
 + Gentamycin + Metronidazole
 Other
 No

If "Other", please describe the following:

- Type of antibiotic
- Dosage
- Timing

Expand

6. Wound Characteristics

- Record the wound measurement details here in centimeters
- OTA wound classification performed by surgeon

Wound Measurement	
Wound measurement length in centimeters (Measure the maximum dimension)	
* must provide value	
OTA Wound Classification	
Skin:	
 Laceration with edges that approximate  Laceration with edges that do not approximate  Laceration associated with extensive degloving	
reset	
Muscle:	
 No appreciable muscle necrosis, or some injury with function intact  Loss of muscle but remains functional, or localized necrosis in injured area that requires excision  Dead muscle, loss of function, partial or complete compartment excision, complete disruption of muscle-tendon unit, muscle injury not approximatable	
reset	
Arterial:	
 No injury  Injury, no ischemia  Injury with distal ischemia	
reset	
Contamination:	
 None or minimal contamination  Surface contamination (not ground in)  Contaminant embedded in bone or deep soft tissues or high risk environmental conditions (barnyard, fecal, dirty water, etc.)	
reset	
Bone Loss:	
 None  Bone loss, but still some contact between proximal and distal fragments  Segmental bone loss	
reset	

6. 3 Baseline Image Upload

Oftentimes, there are differences in how the patient's registration information is registered into the system. If it is not possible to find a patient using his last name, try using the middle or first names or using different spellings. It is also possible to search by MRN or date of x-ray. It is standard policy at MOI that all patients who will get operated at MOI receive x-ray imaging prior to and after the operation. This applies even if the patient arrives at MOI with x-rays taken at another hospital. Therefore, the x-rays should be in the system even if it is difficult to find the x-rays on the computer. Try different search criteria.

It is also of note that desktops in the radiology department immediately adjacent to the x-ray machine which are connected to the machines that digitally scan the x-rays have their images erased on a regular basis. ClearCanvas, however, stores the images on a server indefinitely.

If the x-rays need to be redone, a note should be made in REDCAP

1. The consent form, pre-op x rays, and post-op x-rays should be uploaded as soon as they are available.
 - a. There is an option to upload extra images if they are available. Check on the Extra Image #, describe the image, and upload it by pressing on the “Upload document” link
 - b. Upload any extra images that may be useful for UCSF during review

Baseline Image Upload	
Please upload the signed consent document here	 Upload document
Upload PRE-OP AP view:	 Upload document
Upload PRE-OP Lateral view:	 Upload document
Upload POST-OP AP view:	 Upload document
Upload POST-OP Lateral view:	 Upload document
Check here for any extra images that need to be uploaded:	 Extra Image #1  Extra Image #2  Extra Image #3  Extra Image #4  Extra Image #5  Extra Image #6
Describe what Extra Image #1 is:	
Upload Extra Image #1:	 Upload document

2. The following questions will be used to evaluate the images at baseline
 - a. While the option “X-rays not adequate” has been provided, please refrain from using this answer choice as much as possible in order to maximize the amount of data obtained from the images.

Fracture Classification

- A1 Simple Spiral
- A2 Simple Oblique ($\geq 30^\circ$)
- A3 Simple Transverse ($\leq 30^\circ$)
- B1 Wedge Spiral
- B2 Wedge Bending
- B3 Wedge Fragment
- C1 Complex Spiral
- C2 Complex Segmental
- C3 Complex Irregular
- X-rays not adequate

[reset](#)

Proximal (0%) 50% Distal (100%)

Location (continuous)

Click bar above and then drag to set response

50%

[reset](#)

Number of Cortices Proximally

"N/A" if x-rays not adequate

Number of Cortices Distally

"N/A" if x-rays not adequate

Coronal alignment

- < 5 degrees
- 5-10 degrees
- > 10 degrees
- X-rays not adequate

[reset](#)

Degrees coronal angulation (Continuous)

"N/A" if x-rays not adequate

Direction of angulation

- Varus
- Valgus
- X-rays not adequate

[reset](#)

Sagittal alignment	 < 5 degrees  5-10 degrees  >10 degrees  Radiographs not adequate	reset
Degrees sagittal angulation (Continuous)	 "N/A" if x-rays not adequate	
Direction of Sagittal Angulation	 Procurvatum  Recurvatum  X-rays not adequate	reset
Translation as percentage of shaft width	 0-5  5-10  10-15  >15  X-rays not adequate	reset
Winquist-classification	 Type I - Minimal or no comminution; if comminution is present, there is involvement of 25% or less of the bony circumference  Type II - Comminuted fragments involve up to 50% of the width of the bone  Type III - Comminuted fragment involves more than 50% of the width of the bone; leaves only a small area of contact between the proximal and distal fragments  Type IV - Comminution involves the entire bony circumference; no cortical contact  X-rays not adequate	reset
Bone loss?	 None  Bone missing or devascularized bone fragments, but still some contact between proximal and distal fragments  Segmental bone loss  X-rays not adequate	reset
Is the bone loss >50% of the circumference?	 Yes  No  X-rays not adequate	reset
Length of segment with bone loss	 "N/A" if x-rays not adequate	

